The consent designee must verify the participant physically signed the consent document either by viewing via video conference, obtaining a photo of the signed consent document; or obtaining verbal confirmation from the participant that he/she signed the consent form or agreed to participate electronically. The participant will sign and date/time the informed consent document. The document is then mailed, emailed or faxed to the consent designee. The participant will be asked to return the original signed document on their first in person visit. If the Informed Consent form is mailed to the consent designee by the participant the IRB-approved consent designee will sign the copy, which they possess after the participant has acknowledged signature on their copy. Once the original is received by the consent designee the copies will be attached to make a single document. In all other instances, once received, the IRB-approved consent designee signs, dates/times the informed consent document.

After the Informed Consent process is completed, the IRB approved study team member files the consent document in EPIC, including a note confirming the consent process. The entire consent document is also then filed in the research record.

To the extent possible, assessment instruments will be completed remotely, either by interview with the study coordinator or on paper to be returned with the signed consent form.

Assessment instruments include the following. The MINI International Neuropsychiatric Interview 7.0 (Sheehan et al., 1998) will be used to assess the presence/absence of alcohol or other substance use disorders, as well as mood, anxiety and psychotic disorders to establish

study eligibility. The pattern, amount and route of administration of alcohol use are characterized using the 90-day Time Line Follow Back (TLFB) (Sobell and Sobell, 2003; Robinson et al., 2014). Subjects complete the Alcohol Use Disorders Identification Test (AUDIT) (Bohn et al., 1995) to characterize alcohol-related problems. The Fagerström Test for Nicotine Dependence (FNDT) (Heatherton et al., 1991) characterizes smoking quantity/frequency and severity of nicotine dependence. The Shipley-2 Vocabulary evaluation and or the Rapid Estimate of Adult Literacy in Medicine (REALM Health Literacy Test) will be used to determine reading grade level.

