MIFE has a rapid onset of action and achieves peak plasma levels within 1 - 2 hrs of oral dosing. Peak plasma levels and bioavailability increase as a function of dose but are not directly proportional to dose. However, plasma concentrations of MIFE metabolites do increase in direct proportion to dose; metabolites have antiglucocorticoid activity and contribute to long-acting drug effects (Pomara et al., 2002). MIFE is effective with once-a-day dosing. The half-life is 40 hrs following a single dose and 84.6 hrs following multiple doses. Following discontinuation of MIFE, plasma levels are detectable for up to 2 weeks (Heikinheimo et al., 2003). For this study, we selected to use the high MIFE dose of 1200mg, based on recent clinical trials for other neuropsychiatric disorders associated with HPA-axis dysfunction, and that 1200 mg MIFE has been safely administered over extended periods (MIFE Investigator Brochure, Corcept Therapeutics). This study only exposes subjects to MIFE for up to 6 days. We are not planning to reduce MIFE dose during such a brief treatment period. If a subject experiences significant medication side-effects or any serious adverse event or if the participant declines to continue medication, then we will discontinue that participant from the study. It

should be noted that inpatient subjects are under continuous nursing observation throughout the CRU stay and thus adverse events can be identified and addressed rapidly. HC subjects will be instructed to call the study doctor if they have any adverse events. Subjects will be randomized to active MIFE and placebo on a 2:1 ratio.

In the proposed study, MIFE will be administered under an IND ([name] 124365). MIFE (300 mg) and matching placebo will be provided by Corcept Therapeutics, Menlo Park, CA. We will overencapsulate the medication and placebo as necessary. The Johns Hopkins Bayview Investigational Drug Services (IDS) will maintain the inventory and dispense the medication. MIFE absorption and elimination are not affected by age, body weight, BMI, race or sex (Mifepristone Investigator Brochure, Corcept Therapeutics).

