- c. Justification and safety information if non-FDA approved drugs without an IND will be administered.

During the alcohol sensitivity session, subjects will drink 3 doses of alcohol intended to bring their terminal BrAL to 0.10 mg/dL. Also, at the conclusion of the AMR session, participants can consume up to 5 standard drinks of their preferred alcohol type/brand, based on the number of alcohol reinforcers earned during the session. Beverages containing more than 7% alcohol are not regulated by the FDA; they are regulated by the Bureau of Alcohol, Tobacco, Firearms and Explosives. These beverages are legally sold to adults.

7. Study Statistics

- a. Primary outcome variables:

- adverse events and side-effects;

- fMRI changes in re-FC and CA across brain regions under GR regulatory control;
- Reduction in TSST-induced alcohol motivation and drinking;
- cardiovascular responses (HR, BP, ECG) during alcohol sensitivity sessions;
- alcohol euphoric and sedating effects during sensitivity sessions using VAS and Adjective Scales.

b. Secondary outcome variables will examine the effects of MIFE on a variety of psychological measures during alcohol abstinence, alcohol sensitivity sessions and outpatient visits. Secondary outcome measures include:

- Craving for alcohol during the inpatient stay, assessed using VAS, PACS, OCDS, and AUQ;
- Alcohol withdrawal symptom severity, assessed using the CIWA-Ar;
- Mood and personality assessments during the inpatient stay (BPRS, BDI, and BAI);
- Alcohol use during the outpatient follow-up, assessed using timeline followback self-report and PEth levels.

c. Statistical plan including sample size justification and interim data analysis.

Primary and secondary outcome variables will undergo data cleansing and Corrective/Preventive Measures based confirmation of accuracy and missing data. We will perform exploratory data analyses initially (stem-leaf displays, box plots, histograms, and Q-Q plots) and, if necessary, appropriate data transformations will be performed.

Power analyses: All power estimates are based on type I error =0.05, Power > 0.8. Specific aims are to compare GR antagonism versus placebo for:

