Aim 2. Reduction of alcohol withdrawal symptoms and craving, and improvement in low mood during early alcohol abstinence. Power for this aim was based on Vendruscolo et al (2015) (Fig 2A) in which MIFE effects were examined on VAS craving scores. Our hypotheses test if placebo (size = n) is different from MIFE. Comparing placebo effects (mean=11.5 (SD=2.1) to active drug effects (mean=9.3 (SD=2.2), total sample size required for the proposed aim is 39 (i.e.,20 in each group).

Aim 3. Reduction of stress-induced alcohol motivation and drinking. Power for this aim was based on Vendruscolo et al (2015) (Fig 2B) in which MIFE effects were examined on drinking during an outpatient treatment phase of the study. This calculation is based on between-subject calculation which overestimates the sample size requirement. Comparing placebo effects (mean (SEM) = 38.0 (10.2)) to active drug effects (mean (SD) = 27.5 (10.2)), total sample size required is 32. Using data from our AMR session in which mean number of drinks is 4.33 (sd = 3.17), we are powered to observe a 50% or greater reduction in drinks earned within the session.

Aim 4. Reduction of alcohol reward and sensitivity. Based on our preliminary data (4A1, Aim 3) and a sample of 50 GR antagonist vs 25 placebo subjects, we are powered to detect a difference of 3.0 degrees (3.3%) in peak skin temperature. Further, using data from our current alcohol sensitivity procedure (mean peak VAS total=168 (SD=118); mean peak liking=47.9 (SD=36.9)), we are powered to observe a 45 - 50% or greater reduction in alcohol subjective effects.

Aim 5. Side-effects. Power calculation is based on the assumption that the number of side-effect reports and adverse events follows a Poisson distribution. In preliminary data (Concept Investigator Brochure), an average of 12 events was reported in MIFE treated subjects. We estimate that 22 subjects in each group will give power > 0.8 for this statistical test.

Statistical Analyses: For aims 1 – 4, AUD and HC subjects will be separately grouped.

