Aim 3. AMR variables include: total number of alcohol drinks earned; total number of responses during the 60-minute session; distribution of responses for alcohol versus money; progressive ratio breakpoint for alcohol (maximum completed ratio value); response rate (responses/min) and response latency to compete the ratio for alcohol and money. We also measure alcohol craving using the Tiffany Craving Scale; these data will be summarized using peak score and area under the curve. The normality of the outcome measures will be examined first and two sample t-test, or equivalent non-parametric methods will be used to compare the outcomes between GR antagonist-treated group and placebo-treated group.

Aim 4: Subjective and physiological data will be collected repeatedly during the alcohol sensitivity session. We will test outcome measures between the two groups using mixed-effect linear regression with random intercept. Baseline measures will be examined as potential confounding factors and added to the model if needed. We will summarize the baseline adjusted area under the curve and peak values of the outcome measures and compare between the two groups using repeated measure ANCOVA model.

Aim 5: We use the SAFTEE to collect comprehensive side-effect information. We will construct negative binomial generalized linear regression model with the number of events as the dependent variable and grouping and other covariates as independent variables. The model will give the difference in the logs of expected numbers of side effect events between the two treatment groups. We will then also make comparisons taking into consideration the duration and severity of the side effects, which are both collected in SAFTEE for each reported side effect event. A summary side-effect score will be calculated as the sum of the duration multiplying the severity of each side effect event.

Secondary analyses: Another objective of this study is to generate power estimation for a full-size future clinical trial.

d. Early stopping rules.

Individual subjects will be discontinued from the protocol if they experience a moderate-to-severe adverse reaction to MIFE. They also will be discontinued for repeated rule violations on the CRU. The study will be discontinued if there is a pattern of MIFE-related AEs or SAEs.

8. Risks

a. Medical risks, listing all procedures, their major and minor risks and expected frequency.

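### Aim 3 tests drinks earned without covariates, although pre-randomisation drinking is already recorded; a prespecified ANCOVA would be a cheap gain in precision of uncertain size

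*Combined protocol and SAP*

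**What the plan says.** Section 7c, Statistical Analyses, Aim 3 lists the variables from the alcohol motivated responding (AMR) session, including drinks earned and peak and area under the curve for craving. For the comparison of active with placebo it then states: "The normality of the outcome measures will be examined first and two sample t-test, or equivalent non-parametric methods will be used to compare the outcomes". It names no covariate.

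The other aims in the same section differ. Aim 1 adds confounders if necessary, Aim 2 follows the same kind of t-test or rank test with an ANCOVA, Aim 4 adds baseline measures if needed, and Aim 5 includes other covariates in its count model. No general sentence extends adjustment to Aim 3.

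Section 7a lists stress-induced alcohol motivation and drinking among the primary outcomes. Section 4a (Assessment) covers drinking history at entry: "alcohol use are characterized using the 90-day Time Line Follow Back (TLFB"). The Aim 1 analysis text already reduces that calendar to drinking days, binge days and drinks per drinking day.

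For power, Section 7c says "All power estimates are based on type I error =0.05, Power > 0.8". For Aim 3 it takes a mean of 4.33 and an SD of 3.17 from the investigators' own AMR data and concludes: "we are powered to observe a 50% or greater reduction in drinks earned within the session".

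**The concern.** Only one AMR session is described, on day 5 under study drug, so drinks earned has no baseline of its own. The drinking calendar is the nearest pre-randomisation measure of drinking that the plan already summarises. If it predicts drinks earned, adjusting for it shrinks the residual variance and accounts for chance differences between arms in drinking history. That would help with 25 placebo subjects and a primary outcome whose stated detectable effect is as large as a halving. What is at stake is precision, not bias.

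**Working it through.** **Inputs from the documents**
- Type I error 0.05 and target power above 0.8 (Section 7c, Power analyses).
- Mean 4.33, SD 3.17 and a 50% reduction (Section 7c, Power analyses, Aim 3).
- Allocation: "Subjects will be randomized to active MIFE and placebo on a 2:1 ratio" (Section 4a, MIFE Administration). Only AUD subjects do the AMR session. With 75 of them this gives "a sample of 50 GR antagonist vs 25 placebo subjects", as stated under Aim 4.
- Completion above 90% (Section 5).

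**Assumptions**
- Two-sided test. Aim 3 does not state sidedness; the Aim 2 wording, "Our hypotheses test if placebo (size = n) is different from MIFE", is non-directional.
- The same SD in both arms.
- Joint correlation *r* of the covariates with drinks earned. The documents do not give it, so 0.1 to 0.5 is shown.

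**Step 1: the plan's own figure.** The difference is 0.5 × 4.33 = 2.165, so d = 2.165 / 3.17 = 0.683. The noncentrality is d × √(50 × 25 / 75) = 0.683 × 4.082 = 2.79. With 73 degrees of freedom, power is 78.6% by the noncentral t and 79.6% by the normal formula. The reduction detectable at 80% power is 50.9% (t) or 50.2% (normal). The stated 50% therefore reproduces to rounding.

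**Step 2: with covariates.** The residual SD becomes 3.17 × √(1 − r²), and two degrees of freedom are spent (71 left). Power for the same 2.165 difference, by the noncentral t:

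| Joint r (assumed) | Residual SD | Power at 50:25 | Power at 45:22 |
|---|---|---|---|
| unadjusted | 3.17 | 78.6% | 73.4% |
| 0.1 | 3.154 | 78.9% | 73.8% |
| 0.2 | 3.106 | 80.2% | 75.1% |
| 0.3 | 3.024 | 82.2% | 77.3% |
| 0.4 | 2.905 | 85.1% | 80.5% |
| 0.5 | 2.745 | 88.8% | 84.7% |

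The 45:22 column is a slightly pessimistic bound: 67 / 75 = 89.3%, whereas the plan reports completion above 90%.

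**Step 3: cost if the covariates are useless.** At r = 0, power at 50:25 is 78.5% with two covariates against 78.6% without.

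**Step 4: sensitivity to the equal-SD assumption.** Earnings come from at most 10 half-drink sets, so the outcome is a bounded count. Take a 0–10 beta-binomial that matches 4.33 and 3.17 on placebo, and halve the mean on drug with the same overdispersion (an assumption). The drug-arm SD falls to about 2.64. Simulated unadjusted power at 50:25 is then about 81% to 86%, depending on whether a Welch, pooled t or rank test is used.

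**Step 5: units.** On a 0–5 standard-drink scale with mean 4.33, the SD cannot exceed √(4.33 × 0.67) = 1.70, so 3.17 does not fit that scale. On a 0–10 half-drink count the limit is √(4.33 × 5.67) = 4.95, so it fits. Power is unaffected if mean and SD share a unit, but the plan should name it.

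**The case against.** **The unadjusted test is valid.** This stands. In a randomised comparison it is unbiased and its type I error already allows for chance imbalance. The case for adjustment is efficiency, in a Phase I study seeking preliminary evidence of efficacy.

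**The endpoint is not shown to be underpowered.** A reader might infer from 78.6% that the plan places Aim 3 at the edge of its power or misses its target. The documents do not support that. The 50% figure is a minimum detectable effect, which lies near 80% power by construction. It reproduces to rounding, and Step 4 shows that the small shortfall depends on equal SDs. The other Aim 3 calculation, a total of 32, offers little reassurance either way: it concerns outpatient drinking and labels one spread as SEM and the other as SD.

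**The correlation may be low.** This stands, and it sets the size of the point. AUD entry requires heavy drinking, at least five binges in 30 days and a PEth threshold, which narrows the range of the drinking calendar. Earnings are capped, and the task is a choice between alcohol and money after stress and supervised abstinence, not usual intake. It would go too far to call drinking history a strong predictor.

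**Sex is a weak covariate.** It is tempting to argue that fixed servings make sex predict intake through body size. But drinks are earned during the session and handed over only at its end, so beyond the half-drink primer that mechanism cannot limit earning. Entry thresholds also differ by sex, so sex overlaps with drinking level. It should be optional.

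**The normality check does not prevent adjustment.** A reader might infer that it does. Aim 2 has the same check and still adds an ANCOVA.

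**Conclusion.** Aim 3 is the only aim without provision for covariates, and it covers a primary outcome for which a pre-randomisation drinking measure is already collected. Prespecified adjustment would be a cheap improvement; its absence is not an error in the plan. At 50:25, power moves from 78.6% to between 78.9% (r = 0.1) and 88.8% (r = 0.5), a gain of 0.3 to 10.2 percentage points. These figures rest on a two-sided test, a common SD of 3.17 and an assumed r. The size of the gain cannot be settled from the documents; that the cost is very small can be.

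**What to change.** Before unblinding, make the main Aim 3 analysis an ANCOVA of alcohol drinks earned on arm, with one named calendar summary, drinks per drinking day, as covariate and sex as an optional second. State the unit (half-drink reinforcers or standard drinks). Because the outcome is a bounded count, base inference on robust standard errors or a permutation test, fixed in advance, in place of a choice made after a normality check. Keep the unadjusted comparison as a sensitivity analysis.

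For craving peak and area under the curve, adjust for a pre-drug craving rating already collected, such as the rating in the day 1 cue scan, which precedes randomisation and dosing. This is closer to the outcome than drinking history and sex. The craving rating at the start of the AMR session is taken under drug and should not serve as the baseline.

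The cost is a few sentences in Section 7c and one or two degrees of freedom. No new data are needed.

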Mifepristone (MIFE), a competitive antagonist at the glucocorticoid receptor (GR), is FDA approved or under investigation for treatment of several endocrine and psychiatric disorders. Preclinical studies have shown that MIFE attenuates alcohol-induced mesolimbic DA neurotransmission in mice and reduces voluntary alcohol intake in rats. In alcohol dependent rodents, MIFE blocks the escalation of alcohol intake and compulsive drug-seeking responses during abstinence; it also reduces alcohol-withdrawal induced hyper-excitability and memory deficits. There is a single human study of MIFE for AUD treatment, showing MIFE reduces alcohol cue-induced craving in alcohol dependent subjects. Over time, MIFE should permit “healing” of dopaminergic neurotransmission and other drug-seeking circuitry dysregulated from excessive exposure to cortisol.

We are proposing a Phase I study of MIFE that examines safety, drug-drug interactions, and preliminary evidence of efficacy in reduction of alcohol effects. We will compare the effects of active and placebo MIFE on: 1) fMRI measures of functional connectivity (FC) and alcohol cue-induced brain activation (CA) focused on brain reward and stress pathways, 2) alcohol craving and withdrawal symptoms during alcohol abstinence on the CRU; 3) stress-induced alcohol motivated responding, and 4) alcohol sensitivity/reward. Also, using a within-subject design, we will assess changes in fMRI before and after MIFE administration. Subjects will receive up to 1200 mg MIFE or matching placebo daily over a 6 day period. Age-matched healthy control subjects will also undergo MIFE dosing over a 4 day period and fMRI procedures on an outpatient basis. We predict that MIFE treatment will decrease alcohol withdrawal

symptoms, alcohol motivated responding following stress and subjective experiences of high and positive alcohol effects compared to placebo.

2. Objectives (include all primary and secondary objectives)

Primary aim: The primary study objective is to determine MIFE effects in AUD and HC persons on a variety of alcohol-related measures. We will examine if there are significant interactions between MIFE treatment concurrent with alcohol administration by measuring subjective responses, adverse events and cardiovascular responses (heart rate (HR), blood pressure (BP)), compared to placebo. We also will examine MIFE effects on fMRI, alcohol withdrawal symptoms and craving, and alcohol motivated responding.

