Specific aims are to compare GR antagonism versus placebo for:

1. Changes in resting state FC and CA across key brain regions, focused on nucleus accumbens, amygdala and prefrontal cortex. Hypothesis 1a. GR antagonism will normalize the AUD resting state FC and CA to more closely resemble HC scans. Hypothesis 1b. Magnitude of FC and CA normalization induced by GR antagonism will predict the magnitude of reductions in self-reported CRU alcohol craving and withdrawal in AUD subjects. Hypothesis 1c: The extent of FC and CA dysregulation on day 1 is related to alcohol exposure history.
2. Reduction of alcohol withdrawal symptoms and craving and improvement in low mood during early alcohol abstinence. Hypothesis 2a: GR antagonism will decrease alcohol withdrawal symptoms and craving compared to placebo. Hypothesis 2b: GR antagonism will improve negative mood relative to placebo.
3. Reduction of stress-induced alcohol motivated responding. Hypothesis 3a: Compared to placebo, GR antagonism will decrease alcohol craving and the number of earned drinks following social stress. Hypothesis 3b. The magnitude of FC and CA changes induced by GR antagonism will predict number of drinks earned following stress.
4. Reduction of alcohol sensitivity and reward. Hypothesis 4a: Compared to placebo, GR antagonism will reduce the positive subjective responses and attenuate alcohol-induced increases in heart rate and skin temperature following alcohol administration. Hypothesis 4b: Magnitude of FC and CA changes induced by GR antagonism will predict intensity of self-reported alcohol subjective and physiological effects.
5. Side-effects will be closely monitored in both AUD and HC participants.

3. Background (briefly describe pre-clinical and clinical data, current experience with procedures, drug or device, and any other relevant information to justify the research)

Mechanisms through which cortisol may influence drug related behaviors.

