Daily at 8:00 pm, participants will complete self-reports of alcohol craving, including Visual Analog Scale for alcohol and tobacco craving (VAS); Penn Alcohol Craving Questionnaire (PACS) (Flannery et al., 1999), Beck Depression Inventory-II (BDI-II), Beck Anxiety Inventory (BAI), Obsessive Compulsive Drinking Scale (OCDS), and Alcohol Urge Questionnaire (AUQ). Nursing staff will complete clinician-administered instruments for alcohol withdrawal assessment (see below). Participants will have PRN access to over the counter medications to treat headache, gastrointestinal upset and body aches.

Each day of the CRU stay, the CRU nurse will administer the Systematic Assessment for Treatment of Emergent Events (SAFTEE) (Johnson et al., 2005). This standardized, structured

instrument is specifically adapted for use in substance use disorder clinical trials, to collect information on incidence and severity of medication side effects and adverse events.

To determine if the degree of elevation of CORT in response to GR blockade by MIFE correlates with any of our outcome measures, each morning upon wakening and at bedtime on the CRU, a salivary cortisol sample is obtained. Baseline samples will be collected on day 1, prior to beginning study medications. Measurement of CORT in saliva is not invasive and multiple samples per day are easily obtained. Unlike serum CORT, salivary CORT is unbound to protein and reflects the physiologically relevant fraction. For each sample, subjects chew a pad for 90 sec, which they then place into a capped salivette. Saliva is harvested by centrifugation and stored in a cryotube at -70 until assayed in duplicate (Diagnostic Systems Laboratories; Webster, Texas). The intra- and inter-assay coefficients of variation are below 5%. As we expect variability in CORT within and across MIFE doses, these data will be included in our analyses.

Because MIFE is occasionally associated with hypokalemia, serum potassium level is obtained before study procedures on day 1 and again on day 7 and at the 1 week follow-up visit. Potassium replacement will be addressed as needed.

Outpatient procedures for HC: Healthy control subjects will complete the study as a 4-day outpatient protocol.

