[name] also is responsible for notifying Corcept of (a) any serious and/or unexpected adverse drug experiences (as those terms are defined in 21 C.F.R. § 312.32(a), as amended), and (b) all adverse events of special interest (AESI) that occur during the course of the Study no later than twenty-four (24) hours after receipt of such information. AESI shall mean any of the following events, irrespective of the level of severity:

1. Major adverse cardiovascular events including death related to coronary or cerebrovascular disease, acute myocardial infarction, stroke, and revascularization (coronary or cerebral)
2. Retinopathy
3. Endometrial hyperplasia and/or abnormal vaginal bleeding of any cause

The PI shall notify Corcept of all serious adverse events each time that a report is made to the IRB.

d. Legal risks such as the risks that would be associated with breach of confidentiality.

Our staff is well trained in the matters of confidentiality including maintenance of genotyping information. At present there is no known health implication for the polymorphism under study. Subject numbers will be used to code all data forms for computer entry and storage. Study findings are reported using group data only. No information about subjects will be provided to family members, third persons or organizations. Our study personnel are trained in the protection of human subject confidentiality and are HIPAA trained and certified.

e. Financial risks to the participants.

All costs will be covered by NIAAA grant funds.

9. Benefits

a. Description of the probable benefits for the participant and for society.

This study is conducted for the advancement of science. It will provide critical safety information and examine pharmacokinetic interactions between MIFE and alcohol. It will also determine whether MIFE can be safely used for outpatient treatment of patients who may continue to use alcohol. Finally, it will provide preliminary findings of MIFE effects on alcohol craving, anxiety and intoxication.

This Phase 1 study will provide critical safety information and examine drug-drug interactions between MIFE and alcohol. Outpatient clinical trials that will meet requirements for FDA new drug approval cannot be pursued without this safety information.

10. Payment and Remuneration

a. Detail compensation for participants including possible total compensation, proposed bonus, and any proposed reductions or penalties for not completing the protocol.

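### The primary aim names adverse events as a measure of mifepristone with concurrent alcohol, but no planned analysis compares adverse events under that combination

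*Combined protocol and SAP*

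**What the plan says.** Section 2 (Objectives, primary aim) states: "We will examine if there are significant interactions between MIFE treatment concurrent with alcohol administration by measuring subjective responses, adverse events and cardiovascular responses", compared with placebo. Section 9a (Benefits) repeats the purpose: "This Phase 1 study will provide critical safety information and examine drug-drug interactions between MIFE and alcohol".

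The fifth specific aim is broader and does not mention alcohol: "Side-effects will be closely monitored in both AUD and HC participants". Section 7a lists "adverse events and side-effects" first among the primary outcomes, without a time window or an alcohol condition.

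The Aim 5 analysis in section 7c is a "negative binomial generalized linear regression model with the number of events as the dependent variable and grouping and other covariates as independent variables". Its output is a contrast by treatment: "The model will give the difference in the logs of expected numbers of side effect events between the two treatment groups". A duration-by-severity score follows. On populations, section 7c says only: "For aims 1 – 4, AUD and HC subjects will be separately grouped". Aim 5 is outside that sentence.

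On data collection for AUD participants, General CRU procedures says: "Each day of the CRU stay, the CRU nurse will administer the Systematic Assessment for Treatment of Emergent Events (SAFTEE"). The side-effect instrument is also used at follow-up visits.

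**The concern.** The primary aim names three measures of MIFE with concurrent alcohol: subjective responses, cardiovascular responses and adverse events. The first two are analysed within the alcohol session under Aim 4. Adverse events are not. The only test on them is a MIFE main effect on a count whose time window is not given.

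That contrast can err in both directions if it is read as an answer about alcohol. Ordinary MIFE side effects, unrelated to alcohol, would make it significant. An effect that appears only while participants have alcohol on board would be diluted by alcohol-free days, and by HC participants if they are included. Section 9a says that outpatient trials cannot go ahead without this safety information, so a missing or misread answer has consequences.

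**Working it through.** **1. Where MIFE and a study alcohol dose coincide.** The day 1 drink comes before the scan and the first MIFE dose follows the scan, so that drink does not count. HC participants have no alcohol sessions (Table 1). In AUD participants the overlap is day 5 (a half-drink primer and any drinks earned, at most 5 standard drinks) and day 6 (cumulative dosing to protocol targets). Alcohol-Cue Methods also describes a sip of spirits before scanning, and the second scan is on day 4.

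**2. Measures against analyses.**
- Subjective responses: Aim 4, mixed model within the session.
- Cardiovascular responses: Aim 4, same.
- Adverse events: Aim 5 only, with no session window, alcohol term or exposure offset named.

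**3. The plan's own figure.** Section 7c gives 22 per group for power above 0.8, Poisson counts, and a mean of 12 events on MIFE. No placebo mean is given, so the figure can be neither reproduced nor refuted. For means m1, m0 and dispersion k:

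SE = √[(1/m1 + k)/n1 + (1/m0 + k)/n0]; power = Φ(|ln(m1/m0)|/SE − 1.96).

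With n = 22 per group, k = 0, m1 = 12 and m0 = 9.24: SE = √[(0.0833 + 0.1082)/22] = 0.0933; ln(12/9.24) = 0.261; power = Φ(2.80 − 1.96) = 80%. At placebo means of 9, 10 and 11 the power is 86%, 51% and 16%. The calculation contains nothing about alcohol.

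**4. Dilution.** Assume a constant event rate b per day, 6 MIFE days in AUD, 4 in HC, equal cohorts, follow-up ignored.
- Doubling on day 6 only: AUD (5 + 2)/6 = 1.17; pooled with HC (5 + 2 + 4)/(6 + 4) = 1.10.
- 1.5-fold on days 5 and 6: AUD (4 + 3)/6 = 1.17; pooled (4 + 3 + 4)/10 = 1.10.

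**5. Rejection rates, as ranges.** The time base of the 12-event mean is not stated, so assume b = 0.5 to 2 and k = 0 to 0.5. Arms are 50 and 25 in AUD, 100 and 50 pooled, two-sided 0.05.

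| Truth | Contrast | Rejects |
|---|---|---|
| Doubling on day 6 only | Pooled total | 8–42% |
| | AUD total | 10–61% |
| | AUD day 6 | 49–99% |
| 1.3-fold every day, nothing specific to alcohol | Pooled total | 37% to over 99% |

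Example for b = 1, k = 0.5. Doubling on day 6, pooled: SE = √[(1/5.5 + 0.5)/100 + (1/5 + 0.5)/50] = 0.144; ln 1.1 = 0.095; power 10%. AUD day 6: SE = √[(0.5 + 0.5)/50 + (1 + 0.5)/25] = 0.283; ln 2 = 0.693; power 69%. For 1.3-fold every day, pooled: SE = √[(1/6.5 + 0.5)/100 + (1/5 + 0.5)/50] = 0.143; ln 1.3 = 0.262; rejection 45%.

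**6. Precision of a day 6 comparison.** Treat the window as one day with a true ratio of 1. At b = 2, k = 0: SE = √(0.5/50 + 0.5/25) = 0.173, so the 95% CI is about 0.71 to 1.40. At b = 0.5, k = 0.5: SE = √(2.5/50 + 2.5/25) = 0.387, about 0.47 to 2.14.

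**7. Why not an arm-by-window test against days 2–4.** Hypothesis 2a predicts that MIFE lowers withdrawal symptoms, and those are withdrawal days. Suppose MIFE does nothing on day 6 and cuts days 2–4 events by 30%. With a shared subject effect, variance = 1/(50b) + 1/(25b) + 1/(50·3b·0.7) + 1/(25·3b). At b = 1 this is 0.0829, SE 0.288, z = 0.357/0.288 = 1.24, and the term is significant in 24% of trials. Over b = 0.5 to 2 the range is 14–42%, against a nominal 5%.

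**The case against.** Specific aim 5 asks for side-effect monitoring in both populations, and an overall MIFE–placebo comparison is a proper analysis of that. A reader might infer that Aim 5 tests the wrong hypothesis. It does not: it matches its own aim. The fault is that a different question, in the primary aim, has no analysis.

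A reader might also take the count to be a whole-study total over AUD and HC together. That is the natural reading of a model with no window that lies outside the sentence on separate grouping, but the text states neither. Covariates are left open and could include AUD/HC status. This lowers confidence in the size of the dilution, but does not remove the gap: an AUD-only count still mixes alcohol and alcohol-free days.

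Nor do the documents say that the Aim 5 result will be reported as a drug–alcohol interaction. That misuse is possible, not planned.

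Much of day 6 tolerability is measured in other ways: continuous heart rate, blood pressure every 5 minutes, subjective scales, psychomotor tasks and a hangover scale. This stands, and it limits the gap to event data. The primary aim, however, names adverse events separately.

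Finally, the primary aim's word for interaction need not mean a statistical arm-by-window term. That is right, and step 7 shows why such a term would be a poor main result. Drug exposure also builds up between days 2 and 6: MIFE Administration gives half-lives of 40 hours after a single dose and 84.6 hours after multiple doses. A direct comparison with placebo under alcohol is what the aim asks for.

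**Conclusion.** The point holds as a gap in coverage. As written, the plan leaves the adverse-event part of the primary aim without an analysis, and the Aim 5 contrast cannot fill it. This conclusion rests on the text alone and needs no numerical assumption.

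The size is illustrative. The dilution from 2.0 (day 6) or 1.5 (days 5 and 6) to 1.17 and 1.10 assumes a constant daily rate and a count over all dosing days. The rejection rates depend on assumed event rates and dispersion, and should be quoted only as ranges. The direction is the same throughout the range: the overall count is weak against an effect confined to the alcohol session and can be significant without one. The change should be made before unblinding; nothing in the design has to alter.

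**What to change.** - Keep Aim 5 as the general tolerability analysis. State its window and whether AUD and HC are combined, and state that it is not to be interpreted as a drug–alcohol result.
- Add an AUD-only comparison of side-effect events on the alcohol-session days. The main comparison is day 6 through the day 7 assessment, because the alcohol dosing there is set by protocol. Report day 5 alongside, since alcohol intake on that day is itself an outcome that MIFE is expected to change.
- Use a negative binomial model with arm as the factor and log(days) as offset, and report the MIFE/placebo rate ratio with its 95% CI. Assign events by daily record: the documents mention duration and severity, but not onset time, so a cut-off at the first drink may not be supported.
- Treat any arm-by-window comparison with days 2–4 as supportive, and do not label it the MIFE–alcohol interaction.

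The cost is some SAP wording and one model on data already collected every CRU day. There are two drawbacks. Few events fall in the window, so the interval will be wide (step 6). Participants removed earlier for moderate or severe adverse events (section 4f) are not represented, so the number removed before day 6 should be given by arm.
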